#### • Biomarker Research:

This study will measure biomarkers including 8-hydroxy-2-deoxyguanosine (8-OHdG), malondialdehyde (MDA), superoxide dismutase (SOD), catalase (CAT), nuclear factor kappa B (NF-κB), tumor necrosis factor-α (TNF-α), interleukin 6 (IL-6), and matrix metalloproteinase 9 (MMP-9). Previous literature indicates that the repetitive ischemia and reperfusion injuries associated with OSA lead to excessive production of reactive oxygen species (ROS), oxidative stress substances (such as 8-OHdG and MDA), and inflammatory precursors (such as TNF-α and IL-6), which damage antioxidant capabilities. Oxidative stress substances can increase ROS levels, which activate NF-κB, a transcription factor that stimulates the production of inflammatory precursors and regulates the transcription of MMPs. The activation of TNF-α, IL-6, and MMP-9 can impair endothelial cell function, potentially leading to cardiovascular disease. Research has shown significant increases in serum levels of 8-OHdG, MDA, NF-κB, TNF-α, IL-6, and MMP-9 in OSA patients, while antioxidant stress substances (SOD and CAT) show significant decreases. MDA, NF-κB, and MMP-9 levels are highly positively correlated with the duration of nocturnal oxygen saturation below 85%, and negatively correlated with the average blood oxygen saturation. Additionally, MMP-9 levels are positively correlated with plasma IL-6 and TNF-α levels. This study aims to understand the correlation between the severity of OSA and cardiovascular disease risk factors and to explore whether surgical and

exercise interventions improve these risk factors.

Objective 4: Investigate the correlation between the severity of OSA and cardiovascular disease risk factors.

Objective 5: Examine whether exercise intervention improves cardiovascular disease risk factors and mental state.

[figure not shown]

Figure 1. Experimental Flow Diagram

Experimental Equipment: Figure 2, Table 1

- A) Primary Outcome Measurements:
- Sleep-related assessments:
- i. PSG (Polysomnography) including sleep quality questionnaires: ESS (Epworth Sleepiness Scale), PSQI (Pittsburgh Sleep Quality Index)
- ii. Drug-induced sleep endoscope examination (DISE)
- Computed Tomography (CT)
- B) Secondary Outcome Measurements:

- Respiratory-related muscle function tests:
- i. Tongue muscle (Genioglossus): Iowa Oral Performance Instrument (Medical LLC, Carnation, WA)
- ii. Masticatory muscle function: Dynamometer
- Mental state assessment: Using the Hospital Anxiety and Depression Scale (HADS) to understand the participant's mood status over the past week.

The Hospital Anxiety and Depression Scale (HADS), developed by Zigmond and Snaith (1983) for outpatient patients with physical illnesses, is a tool for measuring anxiety and depression in patients with physical diseases. The scale has been translated into multiple languages and widely used in clinical and research settings (Quintana et al., 2003). The HADS consists of 14 items: 7 items for anxiety (HAD-A) and 7 items for depression (HAD-D). Each item is scored on a four-point scale (0-3), with separate scores for each subscale. Each subscale has a total score of 21, with higher scores indicating higher levels of anxiety or depression. Scores of 0-7 are considered normal, 8-10 indicate mild, 11-14 indicate moderate, and 15-21 indicate severe anxiety or depression. For each subscale, scores of 0-7 indicate no anxiety or depression, 8-10 indicate mild anxiety or depression, and scores of 11 or more indicate the presence of anxiety or depression (Zigmond & Snaith, 1983).

 Molecular biology tests: Analyzing biomarkers in patient serum and cell experiments, including Flow Cytometry, Western Blot, and Enzyme-Linked Immunosorbent Assay (ELISA).

Control Group (weight loss, CPAP, waiting for mandibular advancement devices

[figure not shown]
Initial Measurements at the Start of the Project

- 1. Sleep-related assessments
- 2. CT
- 3. Drug-induced sleep endoscopy
- 4. Muscle function tests
- 5. Biomarker test
- 6. Mental state assessment

Measurements at Week 6 of the Project Start

- Sleep quality
   questionnaires
- 2. Muscle function tests
- Biomarker test
- 4. Mental state assessment

- 18 of the Project Start
  - Sleep-related assessments
  - 2. CT
  - 3. Drug-induced sleep endoscopy
  - 4. Muscle function tests
  - 5. Biomarker test
  - 6. Mental state assessment

group)

Upper airway surgery (surgery and MFT ! 12-Week Rehabilitation Intervention (MFT Group)

Initial Measurements at the Start of the Project

- 1. Sleep-related assessments
- 2. CT
- Drug-induced 3. sleep endoscopy
- 4. Muscle function tests
- 5. Biomarker test
- 6. Mental state assessment

Measurements at Week 6 of the Project Start

- 1. Sleep quality questionnaires
- 2. Muscle function tests
- 3. Biomarker test
- 4. Mental state assessment

Measurements at Week 18 of the Project Start

- 1. Sleep-related assessments
- CT
- 3. Drug-induced sleep endoscopy
- 4. Muscle function tests
- 5. Biomarker test
- 6. Mental state assessment

Figure 2. Sampling Procedure Description

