#### **Clinical Research:**

According to clinical examination of upper airway collapse sites, multiple interventions, including surgery and neuromuscular re-education training of the pharyngeal dilator muscles, will be implemented. The treatment modalities include sleep surgery and orofacial myofunctional therapy, to investigate their clinical efficacy for OSA. Using G power analysis, with a power level set at 80% and an alpha level at 0.05, the effective sample size is estimated to be about 28 subjects per group. The planned number of subjects for the experiment is 35 per group. The experiment is divided into two groups: the experimental group and the control group. The experimental group includes (1) a post-upper airway surgery group undergoing 12 weeks of orofacial myofunctional therapy (n=35) and (2) an upper airway surgery group (n=35). The control group consists of patients undergoing self-directed weight loss, using CPAP, and waiting for mandibular advancement devices (n=35). Given that the fabrication of mandibular advancement devices takes approximately 3-4 months, relevant measurements will be taken during the waiting period. For patients attempting self-directed weight loss, the principal investigator will inquire in the clinic if they are willing to receive professional weight loss consultation. (1) If the patient is willing, they will be referred to [name] weight loss clinic in the Family Medicine Department. (2) If the patient is unwilling, they will receive self-directed weight loss education materials, and a follow-up appointment will be scheduled 6 weeks later in the ENT clinic to check the weight loss status. If weight

loss is unsatisfactory, research assistant (physical therapist [name]) will arrange bi-weekly visits to measure weight and inquire about dietary status, providing food diaries, weight control diaries from the Family Medicine Department, and exercise diaries to ensure accurate recording and monitoring of weight loss. After 12 weeks, a follow-up appointment in the ENT clinic will confirm the weight loss status. All three groups will undergo pre- and post-intervention measurements and follow-up tests in a longitudinal study design to assess the effectiveness of functional training in physical therapy for post-surgical OSA patients.

**Objective 1:** Compare the different clinical outcomes between the two experimental groups to evaluate the clinical benefits of surgery combined with orofacial myofunctional therapy.

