**Objective 2:** Based on drug-induced sleep endoscopy and CT scans, divide the experimental group into three subgroups: soft palate collapse, tongue base collapse, and hypopharyngeal collapse, and compare which subgroup shows the best clinical benefits from the exercise training.

**Objective 3:** According to sleep study reports, conduct a 2x2 factorial analysis of the experimental group based on sleep cycle (REM and non-REM) and sleep position (supine and non-supine) to compare which subgroup shows the best clinical benefits from the exercise training.

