#### **Statistical analysis:**

Continuous variables are presented as mean and standard deviation (SD), whereas categorical variable is presented as numbers and percentages. Kolmogorov-Smirnov test was used to analyze the normal distribution of the variables. Due to the non-normal distribution, Kruskal–Wallis test and Fisher's exact test was used for continuous and categorical data to compare baseline characteristics among the study groups. Besides, the Wilcoxon signed-rank test was used to compare the pre- and post-differences in demographic characteristics, questionnaire, sleep parameters and the data of CT image. Linear regression model with generalized estimating equations (GEE) was used to estimate (1) the difference in differences and the corresponding 95% confidence intervals (CIs) of pre-treatment to post-treatment changes between the 3 groups and (2) multivariate adjusted effects of time in muscle strengths and biomarkers. The working correlation matrix was defined as unstructured. P < .05 was defined as statistically significant. All the statistical analyses were conducted by using SPSS 17.0.

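### Five instruments are listed as primary, unranked and largely without a named parameter, and every result is judged at P < .05 with no multiplicity or success rule, so the planned 0.05 is not protected

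*Combined protocol and SAP*

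**What the plan says.** Under Experimental Equipment, heading A (primary outcomes), the protocol lists "PSG (Polysomnography) including sleep quality questionnaires: ESS (Epworth Sleepiness Scale), PSQI (Pittsburgh Sleep Quality Index"), then "Drug-induced sleep endoscope examination (DISE"), then CT. ESS and PSQI are named scales. For PSG, DISE and CT no variable is given. The list has no order of importance, no co-primary rule and no rule under which one positive result would suffice.

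The Statistical analysis section sets one threshold for everything: "P < .05 was defined as statistically significant". Its GEE model estimates differences in "pre-treatment to post-treatment changes between the 3 groups" without naming an endpoint or giving any contrast priority. Its pre/post tests cover "questionnaire, sleep parameters and the data of CT image". DISE is not mentioned in that section. It does appear in Objective 2, where it helps to form subgroups: "Based on drug-induced sleep endoscopy and CT scans, divide the experimental group into three subgroups".

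Under Clinical Research, the sample size rests on 80% power and "an alpha level at 0.05, the effective sample size is estimated to be about 28 subjects per group", with 35 per group planned and no endpoint stated. Objective 1 is to "Compare the different clinical outcomes between the two experimental groups".

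The Chinese text has the same primary list and the same threshold, so this is not a translation slip.

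**The concern.** A trial sized at one alpha of 0.05 normally has one test, or a defined family of tests, to which that alpha belongs. Here it belongs to nothing in particular. Someone who follows the plan exactly could test several primary instruments, on several possible PSG or CT variables and across three group comparisons, and report whichever falls below 0.05 as the primary finding. The plan would not have been broken, but the chance of a false primary claim would exceed 5%. This matters because the study separates primary from secondary outcomes, is sized for power, and under Expected Results hopes to guide clinical practice.

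**Working it through.** **Inputs from the documents.** Five instruments listed as primary; threshold 0.05; 28 evaluable and 35 planned per group; 80% power. In Table 1, PSG, DISE and CT have Week 18 as their only visit after baseline.

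**Assumptions, none of them stated in the documents.** One parameter per instrument at Week 18; two-sided tests on the Objective 1 contrast; any one significant result counts as success; no true or confounded group difference; normal test statistics with a common correlation r.

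**The plan's own figure.** The 28 per group cannot be reproduced, because no effect size, SD, test or sidedness is given. Solved backwards at 80% power and alpha 0.05, it implies d = 0.76 for a two-sided two-sample t-test, d = 0.67 for a one-sided one, f = 0.35 for a three-group ANOVA, or dz = 0.55 for a paired test.

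**False-positive chance.** For K independent tests it is 1 − 0.95^K:
- K = 5: 1 − 0.95^5 = 0.226.
- K = 4 (DISE not tested, since the analysis section omits it): 1 − 0.95^4 = 0.185.

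With common correlation r it is 1 − ∫ φ(u) [Φ((c − √r·u)/√(1−r)) − Φ((−c − √r·u)/√(1−r))]^K du, where c = 1.96:

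| Tests | r = 0 | r = 0.5 | r = 0.8 | r = 0.9 |
|---|---|---|---|---|
| 5 | 22.6% | 18.3% | 12.7% | 10.2% |
| 4 | 18.5% | 15.6% | 11.4% | 9.4% |

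Even at r = 0.9 the rate is about twice the nominal 5%. It rises further if several PSG or CT parameters count, or if the other group contrasts do. Five instruments on all three pairwise contrasts make 15 tests, and 1 − 0.95^15 = 0.537 if they are independent.

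**Error under the proposed rule.** If the four secondaries are tested only after a significant primary, any false claim under no effect requires the primary itself to be a false positive, so the rate is 0.05 whatever the correlation. Without the gate, and with independent tests, it is 1 − 0.95 × (1 − 0.0125)^4 = 0.097.

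**Power cost.** The first Holm step is 0.05/4 = 0.0125 over four tests and 0.05/5 = 0.01 over five. Two-sided t-test power, 28 / 35 per group:

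| Assumed d | at 0.05 | at 0.0125 | at 0.01 |
|---|---|---|---|
| 0.67 | 69.2% / 78.9% | 47.5% / 59.5% | 44.2% / 56.3% |
| 0.762 | 80.0% / 88.2% | 60.7% / 73.2% | 57.5% / 70.4% |

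The planned model is GEE, so these t-test figures are a guide only.

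**The case against.** The best reply is that the main comparison is not really open. Objective 1 names the contrast, Week 18 is the only post-baseline visit for PSG, DISE and CT, and the questionnaires are nested under PSG, which could be read as one outcome. It is true that a contrast is named. But Objective 1 attaches no endpoint to it, the analysis section treats all three groups alike, no composite is defined, and Figure 2 schedules the questionnaires at Week 6 without PSG.

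A second reply is that no passage says any single significant result would count as success. That also stands, and it is why the percentages are conditional. Equally, no passage says that it would not count.

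A third is that a rule may sit in pages that were not available here. That cannot be excluded. However, the outcome list and the statistical section are present in both languages, and neither refers to such a rule.

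A reader might also count the Week 6 ESS and PSQI as two further Objective 1 tests, making seven and a larger error rate. The documents do not support this. The Chinese Figure 2 labels the surgical groups' Week 6 visit as post-surgery, training lasts 12 weeks, and 6 + 12 = 18. Week 6 therefore probably precedes training. This is an inference, since no start of training is stated, but it is enough to leave those tests out.

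**Conclusion.** The concern holds. Five instruments are primary without ranking, three of them have no named parameter, and one threshold governs every result, so the plan does not keep its own 0.05. On the Objective 1 contrast the illustrative chance of at least one false positive is 10% to 23% for five tests and 9% to 19% for four, over correlations from 0.9 down to 0, under the assumptions listed in the working.

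Two stronger inferences should be avoided. The figures are not the trial's actual error rate: the documents give neither the correlations nor a success rule, and because participants choose their own group, the groups may differ even if training has no effect. Nor is d = 0.76 the planned effect. It is one of several values consistent with 28 per group, so no claim that the trial is too small follows from it.

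**What to change.** **(a) If outcome data have been seen.** The statistical section is in the past tense and justifies its nonparametric tests by non-normality already found, so this may well be the case. Label any choice of a primary outcome as post hoc. Report all five instruments on the Objective 1 contrast at Week 18, one stated parameter each, with Holm-adjusted P values. Naming a single primary at that stage would not restore a 5% error rate.

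**(b) If they have not.** Name one primary test: one PSG parameter of the sponsor's choice, change from Week 0 to Week 18, surgery plus MFT versus surgery alone, two-sided 0.05, using the GEE difference-in-differences already planned. Make ESS, PSQI, DISE and CT secondary, with one named parameter each on the same contrast. Test them with Holm over the four only if the primary is significant.

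In both cases report everything else with 95% confidence intervals as exploratory.

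**Cost.** Protocol and SAP wording only; no new measurements. Fewer results can be called primary, and under (b) no secondary can be claimed if the primary fails. Holm lowers power: at 28 per group and the assumed effects above, the first step has 47.5% to 60.7% over four tests and 44.2% to 57.5% over five. Other valid schemes exist; what matters is that one is stated. The change deals with multiplicity only and does nothing about confounding from self-chosen groups (Assessment Process).

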**Table 1. Detailed Sampling Description** 

MFT: Y/Surgery: Z/Control: O	Week 0	Week 6	Week 18
Basic Data Collection			
Age, Gender, and Volumetric	Y/Z/O	Y/Z/O	Y/Z/O
Parameters			
Confounding Variables			
Medical History Record	Y/Z/O	Y/Z/O	Y/Z/O
Medication Record	Y/Z/O	Y/Z/O	Y/Z/O
Craniofacial Abnormality	Y/Z/O	Y/Z/O	Y/Z/O
Examination Record			
Sleep Clinical Symptoms Record	Y/Z/O	Y/Z/O	Y/Z/O
CT	Y/Z/O		Y/Z/O
Sleep-related Assessments			
Polysomnography	Y/Z/O		Y/Z/O
Drug-induced sleep endoscopy	Y/Z/O		Y/Z/O
Mental state assessment			
HADS	Y/Z/O	Y/Z/O	Y/Z/O
Muscle function tests			
Tongue	Y/Z/O	Y/Z/O	Y/Z/O
Pharyngeal Lateral Wall Muscles	Y/Z/O	Y/Z/O	Y/Z/O
Masticatory Muscles	Y/Z/O	Y/Z/O	Y/Z/O
Others	Y/Z/O	Y/Z/O	Y/Z/O
Biomarker test	Y/Z/O	Y/Z/O	Y/Z/O

#### **Experimental Procedures and Methods:**

#### (1) Assessment Process:

Experimental Procedures and Testing Items: The experimental steps primarily

follow standard clinical procedures, detailed as follows:

- i. Screening through the sleep clinic to determine if further sleep-related assessments are needed (current clinical procedures).
- ii. Establishing the diagnosis of obstructive sleep apnea syndrome through sleep examinations (current clinical procedures, requiring overnight sleep studies at a sleep center).
- iii. Participants agree to self-weight management, use CPAP, await the fabrication of an anti-snoring dental appliance, or undergo sleep surgery.
- iv. Recruiting clinical participants based on inclusion and exclusion criteria, providing comprehensive study information, and informing participants of their right to withdraw from the study at any time. Participants will complete the consent form and will be orally introduced to the study grouping method during the clinic visit. Participants will choose their group based on personal preference and officially enter the clinical research study.
- v. Using computed tomography (CT) and drug-induced sleep endoscope examination to understand the pre-surgical pharyngeal anatomy.
- vi. Performing tongue muscle function tests, recording the results to understand pre-intervention functional indicators (approximately half an hour).
- vii. Conducting biomarker tests to understand pre-intervention biomarker indicators.
- viii. As detailed in Table 1, measurement parameters include sleep-related assessments, mental state assessments, drug-induced sleep endoscope examination, CT scans, respiratory-related muscle function tests, and biomarker tests. Pre- and post-surgical measurements, as well as follow-up measurements, will be conducted and repeated.
- Assessment Location: NCKU Hospital Physical Therapy Center

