#### 實驗流程及方法:

(1) 評估流程:

● 實驗流程及檢測項目:

實驗執行步驟多屬臨床處置標準流程,其細節如下說明:

- i. 透過睡眠門診篩檢是否需要進一步的睡眠相關檢測 (現行臨床處置流程)
- ii. 透過睡眠檢查確立阻塞性呼吸中止症候群診斷 (現行臨床處置流程,需要在睡眠中心進行過夜睡眠檢查)
- iii. 受試者同意自行減重、使用 CPAP 及等待止鼾牙套製作或進行睡眠外科手術
- iv. 依照收案以及排案條件徵收臨床受試者,提供完整詳細的研究說明,並告知受試 者有權利隨時終止參與計畫,完成受試者同意書填寫,此外也會在門診時口頭介 紹計畫分組方式,受試者將以自身意願決定進入之組別,正式進入臨床人體研究 計畫。
- V. 透過電腦斷層掃描及藥物誘導式睡眠內視鏡檢查,瞭解手術前口咽部解剖結構
- vi. 透過舌肌肌肉檢測,紀錄檢測結果,瞭解受試者介入前功能指標(約需半個小時 左右完成)
- vii. 透過生物標記檢測,瞭解受試者介入前生物標記指標
- viii. 如(表一)說明量測參數包含睡眠相關檢測、精神狀態檢測、藥物誘導式睡眠內 視鏡檢查、電腦斷層掃描、呼吸相關肌肉功能性檢測以及生物標記檢測,並依進 行手術前後量測以及追蹤量測等重複測試。
- 評估地點:成大醫院物理治療中心。
- (2) 研究程序及受試者應配合事項:蒐集受試者的基本資料(身體質量指數、體脂肪)等,再由物理治療師施行實驗相關之肌內功能性測試(肌力參數、姿勢評估)等等,治療計畫分別為手術及術後介入口腔舌咽肌內功能訓練12週,並進行手術前後量測以及追蹤量測等重複測試(圖二)。其量測項目包含睡眠專科醫師進行藥物誘導式的睡眠內視鏡檢查及電腦斷層掃描,睡眠專科技師進行睡眠檢查,專業物理治療師進行舌肌肌內功能檢查,以及專業護理人員血液採集,分別在第0週、計畫開始後或術後第6週和計畫開始後或術後第18週採血,一次採血20c.c,總共採血3次。

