#### 統計分析:

連續變數以均值和標準差(SD)表示,而分類變數以數量和百分比表示。使用 Kolmogorov-Smirnov 檢驗來分析變數的正態分布。由於分布不符合正態分布,對於連續數據和分類數據,分別使用 Kruskal - Wallis 檢驗和 Fisher 精確檢驗來比較研究組之間的基線特徵。此外,使用 Wilcoxon 符號秩檢驗比較人口特徵、問卷、睡眠參數和 CT 圖像數據的前後差異。使用帶有廣義估計方程(GEE)的線性回歸模型來估計(1)治療前後三組間差異的差異及其對應的 95%置信區間(CIs),以及(2)時間對肌肉力量和生物標誌物的多變量調整效果。工作相關矩陣定義為非結構化。P<0.05 被定義為統計學上顯著。所有統計分析均使用 SPSS 17.0 進行。

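### Patients choose their own group, but no covariate adjustment is specified for the between-group difference-in-differences that serves Objective 1

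*Combined protocol and SAP*

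**What the plan says.** **Allocation.** Step iv of the Assessment Process reads: "Participants will choose their group based on personal preference and officially enter the clinical research study". The Chinese version says the same ("受試者將以自身意願決定進入之組別"). No randomisation is described.

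**Key comparison.** Objective 1, under Clinical Research, is to "Compare the different clinical outcomes between the two experimental groups to evaluate the clinical benefits of surgery combined with orofacial myofunctional therapy". The third group is a mixed non-surgical one: "The control group consists of patients undergoing self-directed weight loss, using CPAP, and waiting for mandibular advancement devices (n=35").

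**Analysis.** The Statistical analysis section gives the GEE linear model two uses:

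- (1) "the difference in differences and the corresponding 95% confidence intervals (CIs) of pre-treatment to post-treatment changes between the 3 groups", with no covariate mentioned;
- (2) "multivariate adjusted effects of time in muscle strengths and biomarkers", again with no covariate listed.

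The Chinese version splits them the same way ("時間對肌肉力量和生物標誌物的多變量調整效果"), so this is not a slip of translation. Matching, weighting and propensity scores are not mentioned. Baseline characteristics are compared by test, but no rule says what follows from an imbalance.

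**Data.** Table 1 has a block of confounding variables recorded at every visit, and also collects age and sex. BMI is collected under Research Procedures and Participant Cooperation. Polysomnography (PSG), sleep endoscopy and CT are done at Weeks 0 and 18 only. None of these variables is named in a stated model.

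**The concern.** Patients who opt for twelve weeks of exercise after surgery may differ from those who opt for surgery alone, for example in weight, age or disease severity. If such a factor also predicts improvement after surgery, part of the apparent MFT effect could be created or hidden by who chose it. A difference-in-differences does not protect against this, because the factor acts on the change itself. The baseline tests describe such differences without removing them.

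The adjustment in item (2) does not fill the gap. It concerns effects of time, not a contrast between groups, and it covers only muscle strength and biomarkers. Item (1) is the only between-group analysis of change that the plan states, so what is at stake is the estimate that answers Objective 1.

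**Working it through.** The plan gives no figure for imbalance or bias, so there is none to reproduce. From the documents I use only 28 (effective) and 35 (planned) patients per group and the 5% level. Everything else is assumed: true MFT effect zero, a PSG event index as outcome, and a within-arm SD of change of 16/h.

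**1. Bias and false-positive rate of the unadjusted contrast.** Let *g* be the gap in a Week 0 covariate between the surgical arms, in SD units, and *r* its correlation with change.

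- Bias = *g* × *r* × 16.
- Shift in the test statistic: δ = *g* × *r* / √(2/*n*), where √(2/28) = 0.267 and √(2/35) = 0.239.
- Rejection rate ≈ 1 − Φ(1.96 − δ) + Φ(−1.96 − δ).

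| *g* | *r* | Bias (/h) | Rejects, n = 28 | Rejects, n = 35 |
|---|---|---|---|---|
| 0.1 | 0.1 | 0.16 | 5.0% | 5.0% |
| 0.2 | 0.2 | 0.64 | 5.3% | 5.3% |
| 0.25 | 0.3 | 1.2 | 5.9% | 6.1% |
| 0.5 | 0.3 | 2.4 | 8.7% | 9.6% |
| 0.5 | 0.5 | 4.0 | 15.5% | 18.2% |
| 0.75 | 0.5 | 6.0 | 28.9% | 34.8% |

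Simulation (10,000 trials per scenario) agrees. At *g* = *r* = 0.5 the unadjusted contrast rejects 15.0% (n = 28) and 17.7% (n = 35). With the covariate-by-time term in the two surgical arms, bias is about 0 and rejection 4.8% and 4.7%.

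**2. Why main effects are not enough.** With two complete visits, a fixed Week 0 covariate entered as a main effect has the same value at both visits and cancels from the change. In one simulated three-group data set the MFT-by-time estimate was 1.725 without the covariate, 1.725 with it as a main effect, and −0.710 with a covariate-by-time term in the two surgical arms.

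**3. Why the two surgical arms.** If the covariate is unrelated to change in the controls (a deliberately extreme case), one common slope across three groups leaves 1.3/h of the 3.9–4.0/h bias. Restricting the model to the surgical arms leaves about 0.

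**4. Adjusting for the outcome's own Week 0 value.** Assume a 10/h baseline gap.

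- *Change proportional to baseline* (50–60% fall): the difference-in-differences is biased by −0.5 × 10 = −5 to −0.6 × 10 = −6/h and rejects 21.5–30.5%. With age, sex, BMI and three collapse-site terms it still rejects 16–22%. The Week 0-adjusted model rejects about 5%.
- *Stable gap*, pre–post correlation 0.6 to 0.8: the difference-in-differences rejects about 5%. The Week 0-adjusted model is biased by about 10 × (1 − 0.6) = 4 to 10 × (1 − 0.8) = 2/h and rejects 9–17%.

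Neither model is safe alone.

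**5. Cost if the covariates predict nothing.** For *k* terms and *N* patients in two arms, the SE ratio is about √[(N − 3)/(N − k − 3)]. With *k* = 4 this is √(53/49) = 1.040 for N = 56 and √(67/63) = 1.031 for N = 70. Simulation gave 3.7% and 2.8%.

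**The case against.** **The plan is silent, not explicitly unadjusted.** This stands. A reader might infer that the sponsor chose an unadjusted contrast. The text says only that a GEE linear model is used, and it lists no covariates for either item. It also does not say which outcomes item (1) covers, so its link to Objective 1 is a reasonable inference, not a statement. Silence still leaves the contrast either unadjusted or adjusted with covariates chosen later.

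**Collapse site is a weak candidate.** This also stands. A reader might infer that patients sort themselves by site. But group choice is step iv, and CT and endoscopy, which define site in Objective 2, follow at step v. Imbalance could still arise by chance or indirectly, which supports a sensitivity analysis rather than three terms in the lead model.

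**The size is wholly assumed.** True. The rejection rates above run from 5%, which is no harm, to about 35%.

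**Adjustment is incomplete.** True. Motivation, a plausible driver of the choice, is not measured. For a PSG outcome, where its own baseline is left out, the adjusted difference-in-differences stays biased if change is proportional to baseline. Several models without a designated lead would also add analytic freedom, so one must be named.

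None of this removes the core point: a self-selected contrast has no stated adjustment although relevant Week 0 data are already collected.

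**Conclusion.** The concern holds in a limited form. Groups are self-selected, no covariate adjustment is specified for the between-group difference-in-differences, and the recorded confounders are named in no model. The estimate for surgery plus MFT versus surgery may therefore be confounded by Week 0 factors that predict change.

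The documents do not support the stronger inference that the estimate is biased by a known amount or in a known direction. The bias may be negligible: about 0.6/h, with no visible effect on the error rate, at a gap of 0.2 SD and correlation 0.2. It would matter at 0.5 and 0.5: about 4/h, with 15–18% false positives. These figures rest on an assumed SD of change of 16/h, a single covariate, two complete visits and no true effect. This should be fixed, but it does not make the trial invalid.

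**What to change.** For the surgery plus MFT versus surgery contrast:

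1. **Lead analysis.** Fit the group-by-time GEE in the two surgical arms with a short fixed list of Week 0 covariates: age, sex, BMI and one named PSG severity index. Enter each as a covariate-by-time term. Omit the index when it is the outcome's own baseline.
2. **Beside it**, show the unadjusted difference-in-differences.
3. **Sensitivity analyses.** Fit a Week 18 model adjusted for the outcome's Week 0 value, stating that it and the lead model rest on different untestable assumptions. Collapse site may be added in a further one.
4. **Labelling.** The Statistical analysis section is in the past tense and already reports a distribution result ("Due to the non-normal distribution"). If outcome data have been examined, call the covariate list post hoc. Describe the result as a non-randomised association with residual confounding, for example by unmeasured motivation.

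**Cost.** Plan wording and changes to the model code; no new data. If the four terms predict nothing, the SE rises by about 3–4% in a two-visit model. Outcomes also measured at Week 6 need more terms (4 × 2 = 8 if visit is categorical), and that case was not costed. The change cannot remove unmeasured confounding.
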